Alternatively, an explanation of why a DMC is not needed

Given that this is a pilot trial of an intervention with minimal risks, we will not retain a data monitoring committee.

21b. Description of any interim analyses and stopping guidelines

Including who will have access to these interim results and make the final decision to terminate the trial

No interim analyses will be conducted. We will employ the following stopping rule for the clinical trial: if there is clear evidence of harm. Although we do not expect any physical harms or serious psychological harms beyond minimal distress, we have several procedures for monitoring harm from the intervention, including asking participants to contact us if they experience any adverse events, offering additional resources to those with very high levels of mental health symptoms and problem drinking that we identify through data monitoring, and providing resources after baseline and at every follow-up time point. We do not expect there to be overwhelming evidence of the harm of the intervention, but we will monitor this and stop the trial if this is indicated. We also do not expect that there will be no likelihood of demonstrated treatment benefit (futility) for the intervention as compared to control.

22. Harms

Plans for collecting, assessing, reporting, and managing solicited and spontaneously reported adverse events and other unintended effects of trial interventions or trial conduct

Potential risks

Risks to the participants in the intervention are not substantial: they will receive a combination of commonly-used evidence-based skills that are similar to those known to be effective with PTSD and high-risk drinking and are thus unlikely to increase distress. The sensitivity of some of the measures poses some psychological risk, as they may be somewhat uncomfortable to complete.

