Reports of suicidal ideation ethically require follow-up by the investigators, and could potentially result in the need to violate confidentiality in order to protect the participants, consistent with ethical guidelines and State and Federal regulations. Thus, this represents a potential limit to confidentiality. It is possible that participants randomized to the assessment only group may experience increased negative affect and alcohol use in their daily lives. At the conclusion of their participation (3 month follow-up) participants who were assigned to the assessment only group will be offered the web-based intervention. In addition, we will offer all participants referrals for additional services. No participants will be excluded from seeking additional services while part of this study.

Protection against risks

We recognize that this is a vulnerable population and have taken a number of steps to protect the patients' rights and welfare. Participants may refuse to answer questions or may withdraw from the study at any time. Participants are also encouraged to contact the investigators at any time to discuss any concerns they might have. [name] is qualified to provide referrals and address concerns related to psychological distress arising through participation in this study.

Trained personnel will be present or on call when specific study procedures take place, though we will make it clear to participants on consent documents and in emails that we may not be able to return calls or emails received during the evening/night time until the next day. Drs. [name], [name], and [name] have training in working with individuals with PTSD, alcohol misuse, and with individuals with chronic and severe suicidality and thus is competent to assess and intervene with these individuals. Drs. [name], [name], and [name] are well-versed in the requirements and procedures for monitoring and reporting adverse events and complaints to the IRB for review within 48 hours, and Drs. [name], [name], and [name] are licensed Clinical Psychologists in the State of Washington competent to handle any adverse psychological events which may arise. They are also well-versed in clinical management and oversight for remotely-conducted clinical trials. [name] has over 12 years of clinical and research experience working with victims of trauma exposure and sexual assault and is well-qualified to assess and treat individuals in crisis.

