All participants, regardless of study or intervention condition, will be offered resources for mental health and rape crisis services. These resources will again be offered to participants after each survey. All participants, regardless of whether they are intervention or control, will be offered these resources. Participants in any of the samples or conditions will not be prevented from seeking additional services for alcohol use or other mental health concerns.

Suicidality. A plan is in place for identifying, contacting, and referring individuals with significant suicidal ideation. Suicide risk is assessed at screening. The study team will take steps to ensure the safety of the participant and others, and participants with high levels of risk will be ineligible to participate in the study. Participants will be told during the consenting process that disclosure of suicidal ideation may necessitate a break of confidentiality. All staff members conducting phone screenings will be trained to assess suicidal risk and intervene with suicidal participants. Disclosure of suicidal ideation will trigger a protocol involving an additional set of questions to assess degree of suicidal risk and appropriate follow-up action tailored to the level of risk. For all non-imminent risk, study staff will engage in safety planning over the phone, but if it is assessed that participant remains an imminent risk for

suicide, we will work with the participant to secure additional mental health support. If a participant refuses to remain safe, we will explain to the participant that we must contact the necessary resources to ensure their safety. We will then contact the appropriate officials who are able to intervene in a suicidal crisis. [name] will be contacted in all such situations. Although suicide is not formally assessed at further assessments, if individuals disclose significant distress or suicidal ideation to their coach, the same procedures will be used. This is consistent with recommended best practices for remote management of suicide risk.

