Potentially-lethal alcohol consumption. A plan is also in place for identifying and referring individuals who report consumption of potentially lethal doses of alcohol (BACs above .30). Specifically, all daily data will be screened immediately upon entry for indication of significant risk based on criteria established in our prior trials of this nature. [name] will be notified within 48 hours upon identification of a participant who meets criteria for elevated BAC. [name] will attempt to reach all participants who report BACs greater than .30 within 48 hours to inform them of their risk and offer referral resources. All such contact will be noted in a tracking database.

Information regarding the potential for a follow-up contact by the investigators to clarify responses or provide information is included in the consent documents. Participants are also informed in the consent form that they are free to seek other services for their alcohol use and can contact us for referrals. This structure is currently in place and approved at both the local and federal level on all existing drinking and drug prevention studies conducted in the Center for the Study of Health and Risk Behaviors.

23. Auditing

Frequency and procedures for auditing trial conduct, if any, and whether the process will be independent from investigators and the sponsor

No auditing will be conducted.

Ethics and Dissemination

24. Research ethics approval

Plans for seeking research ethics committee/institutional review board (REC/IRB) approval

We have obtained ethical approval from the University of Washington IRB.

25. Protocol amendments

Plans for communicating important protocol modifications (eg, changes to eligibility criteria, outcomes, analyses) to relevant parties (eg, investigators, REC/IRBs, trial participants, trial registries, journals, regulators)

Any modifications to the protocol which could impact the conduct of the study, potential benefits to the participants or participant safety, including changes to study objectives, study design, target population, sample sizes, study procedures, or significant administrative aspects, will require a formal amendment to the protocol. This amendment will be approved by the study PI and the IRB prior to implementation.

Administrative changes (i.e., minor corrections and/or clarifications that have no effect on the way the study is conducted) will be documented by the PI, and approved by the IRB if necessary.

26. Consent or assent

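### Targeted harms are monitored in both arms, but adverse events as such reach staff only if volunteered, and no descriptive harms summary by arm is described

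*Combined protocol and SAP*

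**What the plan says.** Section 21a retains no data monitoring committee, on the ground that this is a minimal-risk pilot. Section 21b plans no interim analyses but does set a stopping rule: "We will employ the following stopping rule for the clinical trial: if there is clear evidence of harm". It says "we have several procedures for monitoring harm from the intervention". The first example relies on the participant: "asking participants to contact us if they experience any adverse events". The second relies on the study's own data: "offering additional resources to those with very high levels of mental health symptoms and problem drinking that we identify through data monitoring". The third is giving out resources at baseline and each follow-up. Of overwhelming evidence of harm, section 21b adds: "we will monitor this and stop the trial if this is indicated".

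Section 22 gives the detail:

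- Investigators are described as well versed in "monitoring and reporting adverse events and complaints to the IRB for review within 48 hours".
- On suicidality after screening: "Although suicide is not formally assessed at further assessments, if individuals disclose significant distress or suicidal ideation to their coach", the screening-stage procedure applies, and a designated person is contacted.
- On drinking, "all daily data will be screened immediately upon entry for indication of significant risk". A designated person is notified within 48 hours of a blood alcohol level above .30, and the contact is logged in a tracking database.

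Under sections 11a and 11c, coaches in both arms check mood, well-being and risk at three weekly check-ins offered after an initial call. Under section 18a, surveys take place at baseline, daily during the intervention, post-intervention and at 3 months; the two later surveys assess learning and symptoms. Section 20a covers hypotheses H1 to H5 only.

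**The concern.** Section 22's own prompt asks for plans covering both solicited and spontaneously reported adverse events. The text beneath it describes no solicited method: no standard adverse-event question is mentioned for any survey or check-in. Volunteered reports depend on who chooses to make contact, so they tend to under-count, and counts from two arms are hard to compare. Contact also differs by arm here, because intervention coaches have extra tasks and so more occasions on which a report might be made.

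Two things are at stake. First, the stopping rule turns on evidence of harm, yet the plan does not describe how volunteered events, coach reports and daily-data flags are put together for that judgement. Second, a pilot in a population that section 22 calls vulnerable should hand the next trial a simple account of harms in each arm. Section 22 itself foresees that assessment-only participants may have more negative affect and alcohol use, so the control arm matters too.

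**Working it through.** The plan gives no harms figure to reproduce. The check sets each described route beside what it yields, then sizes the period without contact.

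**Routes described**

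| Route | Who initiates | Arms | Covers adverse events as such? |
|---|---|---|---|
| Participant contacts staff (21b, 22) | Participant | Both | Yes |
| Weekly coach check-in (11a, 11c) | Staff | Both | Mood, well-being and risk; no standard question described |
| Daily data screen (22) | Staff | Both | Signs of significant risk; stated flag is blood alcohol above .30 |
| Symptom and drinking monitoring (21b) | Staff | Not limited to one arm | Very high symptoms or problem drinking |
| Post-intervention and 3-month surveys (18a) | Staff | Both | Learning and symptoms; no adverse-event item described |

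Section 27 lists life events and psychiatric status among the measures but gives no time points. The H5 models in section 20a compare drinking and PTSD by arm at each follow-up; they do not list individual events.

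**Length of daily contact.** Section 11a gives 3 weeks of app use. The payments agree: 20 + 40 + 60 + 21 × 3 + 3 × 10 = 213, the total in section 18b, so there are 21 daily surveys. Coach contact ends between about day 21 and day 28.

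**Share of follow-up with neither a daily survey nor scheduled coach contact**

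- Last survey 3 months after baseline (18a), about 91 days: (91 − 28)/91 = 69% to (91 − 21)/91 = 77%.
- Last survey 3 months after termination (a reading of 18b, where the interval is garbled), about 21 + 91 = 112 days: (112 − 28)/112 = 75% to (112 − 21)/112 = 81%.

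**What incomplete capture could do.** The documents give neither event rates nor capture fractions, so both are assumed. With true risk p and capture fraction c, the chance that an arm of 20 records at least one event is 1 − (1 − pc)^20:

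| Assumed risk | All captured | Half | A quarter |
|---|---|---|---|
| 5% | 64% | 40% | 22% |
| 10% | 88% | 64% | 40% |
| 15% | 96% | 79% | 53% |

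**What a table by arm can show.** For 0/20 the one-sided 95% upper bound is 1 − 0.05^(1/20) = 0.139, or 14%, provided capture is complete. For 2/20 the Clopper-Pearson 95% interval is 1% to 32%.

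**The case against.** The strongest reply is that the foreseeable harms here are distress, suicidality and dangerous drinking, and that staff look for distress and dangerous drinking in both arms. That stands. A reader might infer from the passive adverse-event route that harm goes unmonitored, or that nobody receives the signals. The documents do not support this: coaches monitor risk, daily data are screened, designated staff are notified of suicidality and blood alcohol signals, and reporting to the IRB within 48 hours is covered. The examples in section 21b are also introduced as a partial list.

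H5 already compares drinking and PTSD between arms, so average worsening on those measures would be visible. That also stands. What remains is individual events and harms of other kinds.

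A reader might infer that no adverse-event question will be asked at all. The survey items, coach scripts, consent form and registry outcomes are not in the reviewed text, so the most that can be said is that none is described. Nor do the shares of time without contact say that a like share of events is missed: the 3-month survey may pick some up through symptoms, and participants may call.

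Finally, solicited counts would still be open to reporting differences by arm, because check-ins are only offered and nobody is blinded. True; an identical item reduces this problem without removing it.

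**Conclusion.** The point holds as a cheap improvement to harms ascertainment and reporting. Followed as written, the plan relies on volunteered reports for adverse events outside the targeted harms, most plainly in the 9 to 10 weeks after coach contact and daily surveys end (63 to 70 days; 12 to 13 weeks, or 84 to 91 days, on the post-termination reading). It describes no harms summary by arm for a trial whose only stopping rule concerns harm.

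The extent of under-capture is unknown; the probabilities above rest on assumed rates and capture fractions. In a 40-person pilot the resulting table can only be descriptive. No efficacy estimate or test is affected. The material does not call for a data monitoring committee, a repeat suicidality screen, a significance test on harms or a numerical stopping threshold.

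**What to change.** Add one adverse-event item, worded identically in both arms, to the post-intervention and 3-month surveys, and to the weekly check-in script wherever a check-in takes place. The 3-month item should ask about the whole time since the post-intervention survey. State in section 20 that counts will be reported descriptively by arm, beside the blood alcohol contacts already logged, and in section 21b that the investigator will consider them under the existing stopping rule. Disclosures of suicidal ideation follow the procedure already in section 22. Settle the conflict between sections 18a and 18b on the timing of the last survey.

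The cost is up to 3 check-in and 2 survey asks per participant, (3 + 2) × 40 = 200 in all, one table, and an IRB-approved wording amendment, with no added visits. The downsides are slightly longer contacts, answers that staff must check promptly, weaker recall over about 10 weeks (13 on the post-termination reading), and possible reporting differences by arm in an unblinded trial. If the instruments already contain such an item, the change reduces to stating it and tabulating the answers by arm.
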